10. STATISTICAL ANALYSIS

General approach to data analysis

1. For the main study outcomes length velocity of the infant will be analyzed by predefined hypothesis in multiple arms. However conclusions on this part of the study will be based on formal hypothesis testing.
2. For secondary objectives (weight velocity, length-for-age, weight-for-length, and weight-for-age Z scores) will be analyzed by predefined hypothesis in multiple arms. However conclusions on this part of the study will be based on formal hypothesis testing.

Hypotheses to be tested

Primary

- a) To assess the efficacy of a fortified, balanced energy-protein supplementation intake using a ready-to-use product to lactating women of Mid-upper-arm-circumference (MUAC) of less than 23.0 cm for initial 6 month of exclusive breastfeeding with or without single prophylaxis dose of Azithromycin to infants at day 42 of age, in improving length velocity as the primary outcome at 6 months of age as compared to the standard of care..

Hypothesis to be tested:

H_a = Mean difference in length velocity of $>0.12\text{cm/month}$ to look at comparisons between multiple arms

H_o = Mean difference in length velocity of $\leq 0.12\text{cm/month}$ to look at comparisons between multiple arms

Secondary objective

- a) To assess the efficacy of a fortified, balanced energy-protein supplementation intake using a ready-to-use product to lactating women of Mid-upper-arm-circumference (MUAC) of less than 23.0 cm for initial 6 month of exclusive breastfeeding with or without single prophylaxis dose of Azithromycin to infants at day 42 of age, on weight velocity, length-for-age, weight-for-length, and weight-for-age Z scores as secondary outcome at 6 months of age as compared to the standard of care.

Hypothesis to be tested:

- i. **Growth velocity at 6 months of infant's age**

H_a = Mean difference in growth velocity of $>0.4\text{ gram/kg/day}$ to look at comparisons between multiple arms

- H_o = Mean difference in growth velocity of ≤ 0.4 gram/kg/day to look at comparisons between multiple arms
- ii. **Length-for-Age Z-score (LAZ) at 6 months of infant's age**
 H_a = Mean difference in LAZ >0.5 to look at comparisons between multiple arms
 H_o = Mean difference in LAZ ≤ 0.5 to look at comparisons between multiple arms
 - iii. **Weight-for-Length Z-score (WLZ) at 6 months of infant's age**
 H_a = Mean difference in WLZ >0.5 to look at comparisons between multiple arms

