Data Safety and Monitoring Board of the trial will request an independent statistician to run interim analysis when 50% of the enrollment will complete the 6 months follow-ups in the trial. The analysis will be coded and the findings will on difference in primary, secondary outcomes and Serious Adverse Events will be shared to DSMB in blinded coding. The DSMB will review results from the interim data analysis and will determine whether stopping boundaries have been crossed. Additional interim analyses may be completed and reviewed by the DSMB, per the advisement of the DSMB chair. The DSMB may, at its own discretion, ask the interim analysis to be done earlier or additional interim analyses to be completed on an ad hoc basis.

For any interim analysis, the data management team at the VPT will prepare a blinded, cleaned analysis database. The interim analysis will be conducted on a blinded basis, as follows: Project data team at VPT will prepare and verify interim analysis programs using randomly generated dummy treatment assignments that have no relationship to the true intervention assignments. An independent statistician will subsequently incorporate blinded treatment codes group 1, 2 and 3 for safety end points status. The data team will separately provide treatment codes to the chair of the DSMB in a sealed file. At a minimum, the results to be presented will include a summary of screening and enrollment status, descriptive statistics of baseline variables, summaries of protocol violations, serious adverse events, primary, and secondary growth outcome. Site-specific and overall results will be pooled over treatment groups. DSMB may request other analyses as it deems fit. The DSMB will decide whether or not they wish to open the treatment code envelopes to un-blind themselves.

i. Stopping guidelines / Stopping rules

Based on the trial safety monitoring and interim analysis, the following may be the key decision/s of DSMB pertaining to the trial:

- a) No action needed, trial continues as planned.
- b) Early stopping due, for example, to clear benefit or harm of an intervention/s, uselessness, or external evidence.

- c) Extending recruitment (based on actual control arm response rates being different to predicted rather than on emerging differences) or extending follow-up.
- d) Stopping an arm of the multi-arm trial.
- e) Sanctioning and/or proposing protocol changes

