While stopping rules will be utilized to help the DSMB to assess the justification of trial continuation, the DSMB will take into account the balance of risks and benefits as well as consistency with external evidence. Thus, the DSMB recommendation to continue or discontinue will not be based on any single issue or value in any of the analyses, but a comprehensive analysis taking into account multiple issues around the trial.

The DSMB may recommend termination or modification of the study if:

- i. In an interim analysis, there is strong evidence of a benefit (increases length velocity and/or secondary outcome) from the study intervention (O'Brien Fleming rule, $p < 0.005$).
- ii. In an interim analysis, there is strong evidence of harm (incidence of SAEs) from the study intervention. For harm assessment, no fixed statistical rules will be applied, but the DSMB will holistically consider point estimates and confidence intervals for SAE incidence differences, p-values from appropriate statistical tests and other relevant factors, when determining its recommendation about study continuation or discontinuation.

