10.2. Secondary growth outcomes*

- **'Growth velocity (gm/kg/day) of infant'** at 6 months is define as per Patel Exponential method = $[1000 \times \ln(\text{Weight at 6-month visit} - \text{Weight at baseline})] / (\text{Date of visit of visit at 6-month} - \text{Date of enrollment})$. (4)
- **'Weight gain (gm/month) of infant'** at 6 months is define as = $(\text{weight at 6-month visit} - \text{weight at baseline}) / (\text{Date of visit of visit at 6-month} - \text{Date of enrollment}) * 30.4$.
- **'LAZ, WAZ and WLZ of infant'** at 6 months is define as per WHO z-anthro 2006 guidelines and standard queries. Change in
- **Stunting** at 6-month is define as <-2 SD length for age z score
- **Wasting** at 6-month is define as <-2 SD weight for length z score
- **Underweight** at 6-month is define as <-2 SD weight for age z score
- **'Gain in infant MUAC (cm/month)'**, at 6 months is define as = $(\text{MUAC at 6-month visit} - \text{MUAC at baseline}) / (\text{Date of visit of visit at 6-month} - \text{Date of enrollment}) * 30.4$
- **'Gain in infant head circumference (cm/month)'**, at 6 months is define as = $(\text{head circumference at 6-month visit} - \text{head circumference at baseline}) / (\text{Date of visit of visit at 6-month} - \text{Date of enrollment}) * 30.4$
- **'Maternal weight change Kg/month'**, at 6 months is define as = $(\text{Maternal weight at 6-month visit} - \text{Maternal weight at baseline}) / (\text{Date of visit of visit at 6-month} - \text{Date of enrollment}) * 30.4$
- **'Gain in Maternal MUAC (cm/month)'**, at 6 months is define as = $(\text{MUAC at 6-month visit} - \text{MUAC at baseline}) / (\text{Date of visit of visit at 6-month} - \text{Date of enrollment}) * 30.4$

*All measurements were taken at baseline, then day 27, 56, 89, 114, 143 and 177-179 of infant's age. we allow a window until next follow-up is appeared.

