Data Safety and Monitoring Board of the trial will request an independent statistician to run interim analysis when 50% of the enrollment will complete the 6 months follow-ups in the trial. The analysis will be coded, and the findings will on difference in primary, secondary outcomes and Serious Adverse Events will be shared to DSMB in blinded coding. The DSMB will review results from the interim data analysis and will determine whether stopping boundaries have been crossed. Additional interim analyses may be completed and reviewed by the DSMB, per the advisement of the DSMB chair. The DSMB may, at its own discretion, ask the interim analysis to be done earlier or additional interim analyses to be completed on an ad hoc basis. Based on the trial safety monitoring and interim analysis, the following may be the key decision/s of DSMB pertaining to the trial:

- i. No action needed; trial continues as planned.
- ii. Early stopping due, for example, to clear benefit or harm of an intervention/s, uselessness, or external evidence.
- iii. Extending recruitment (based on actual control arm response rates being different to predicted rather than on emerging differences) or extending follow-up.
- iv. Stopping an arm of the multi-arm trial.
- v. Sanctioning and/or proposing protocol changes

While stopping rules will be utilized to help the DSMB to assess the justification of trial continuation, the DSMB will take into account the balance of risks and benefits as well as consistency with external evidence. Thus, the DSMB recommendation to continue or discontinue will not be based on any single issue or value in any of the analyses, but a comprehensive analysis considering multiple issues around the trial.

The DSMB may recommend termination or modification of the study if:

- i. In an interim analysis, there is strong evidence of a benefit (increases length velocity and/or secondary outcome) from the study intervention (O'Brien Fleming rule, $p < 0.05$).

- ii. In an interim analysis, there is strong evidence of harm (incidence of SAEs) from the study intervention. For harm assessment, no fixed statistical rules will be applied, but the DSMB will holistically consider point estimates and confidence intervals for SAE incidence differences, p-values from appropriate statistical tests and other relevant factors, when determining its recommendation about study continuation or discontinuation.

16. Background characteristics of participants

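### The interim benefit guideline accepts any one unnamed secondary outcome as a ground to stop, without a supporting result on length velocity and without a multiplicity correction

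*Protocol*

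**What the plan says.** Under the stopping guidelines in Protocol section 10, and in the same words in SAP section 15, the DSMB may recommend termination or modification if an interim analysis shows "strong evidence of a benefit (increases length velocity and/or secondary outcome) from the study intervention". The protocol attaches "O'Brien Fleming rule, $p < 0.005" to this criterion and the SAP attaches "O'Brien Fleming rule, $p < 0.05". Neither states whether the p-value is one-sided or two-sided.

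The planned look is to "run interim analysis when 50% of the enrollment will complete the 6 months follow-ups in the trial". The DSMB may also "ask the interim analysis to be done earlier or additional interim analyses to be completed on an ad hoc basis".

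The protocol's secondary objectives for testing are "weight velocity, length-for-age, weight-for-length, and weight-for-age Z scores", four growth outcomes. SAP 10.2 lists twelve: growth velocity, weight gain, LAZ, WAZ, WLZ, stunting, wasting, underweight, infant MUAC gain, head circumference gain, "Maternal weight change Kg/month" and maternal MUAC gain.

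Both documents add that the DSMB's recommendation "will not be based on any single issue or value in any of the analyses".

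**The concern.** As worded, a secondary outcome can meet the benefit criterion alone. Nothing says which secondary outcome counts, for which arm pair, or that length velocity must point the same way. The primary objective and the whole sample size calculation (Protocol section 11, SAP section 6) rest on length velocity, and no secondary outcome has a power calculation.

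Two things are at stake. A stop prompted by a secondary outcome could leave the primary comparison less precise than planned. In addition, each further outcome and arm pair offers another chance to cross the nominal boundary when nothing is going on.

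**Working it through.** **Inputs.** Difference 0.12 cm/month, SD 0.5, one-sided alpha 0.025, 274 evaluable per arm and 319 after 14% dropout, stated power 0.801 (Protocol section 11). Three arm pairs (same section). Thresholds p<0.005 (protocol) and p<0.05 (SAP).

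**Planned size.** SE = 0.5·√(2/274) = 0.0427. Power = Φ(0.12/0.0427 − 1.96) = Φ(2.809 − 1.96) = 0.802, or 0.801 with the t distribution. 274/0.86 = 319. The plan's figures reproduce.

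**Data at the planned look.** Half of 274 is 137 evaluable per arm. Half of 319, if nobody drops out, is about 160.

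- Power at one-sided 0.025: Φ(1.986 − 1.96) = 0.51 at 137; Φ(2.147 − 1.96) = 0.57 at 160.
- 95% half-width, 1.96·0.5·√(2/n): 0.118 at 137 and 0.110 at 160, against 0.084 at 274. At the look it is nearly as large as the target effect.
- To cross two-sided p<0.005 (z = 2.807), length velocity must show at least 2.807·0.5·√(2/n) = 0.170 (137) or 0.157 (160) cm/month. If the true difference is 0.12, the chance of that is 21–25%. The primary would usually not cross even if the design assumption were right, so a crossing on a secondary outcome alone is a realistic path.

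**If enrolled infants are followed to 6 months.** The look comes when half have completed 6 months, so recruitment may have gone on meanwhile. With uniform accrual over T months (T is not given, so this is an assumption), the fraction enrolled at the look is min(1, 0.5 + 6/T), and evaluable n is 274 times that:

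| T (months) | Fraction enrolled | n per arm | Power | 95% half-width |
|---|---|---|---|---|
| 12 | 1.00 | 274 | 80% | 0.084 |
| 18 | 0.83 | 228 | 73% | 0.092 |
| 24 | 0.75 | 206 | 68% | 0.097 |
| 36 | 0.67 | 183 | 63% | 0.103 |

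**Chance of at least one nominal benefit crossing when nothing works.** One look, three arms, three pairs, and normal outcomes with equal correlation 0.3–0.7 (assumed; the documents give none). Thresholds are read as two-sided and only the benefit direction is counted. Each setting used 200,000 simulated trials.

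| Rule | Length velocity alone | With secondary outcomes |
|---|---|---|
| Protocol: p<0.005, 1 + 4 = 5 outcomes | about 0.7% | 2.6–3.4% |
| SAP: p<0.05, 1 + 12 = 13 outcomes | about 6.6% | 28–47% |

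As a rough check on the first column, the Bonferroni ceilings are 3 × 0.0025 = 0.75% and 3 × 0.025 = 7.5%. Extra looks, which both documents allow without limit, would add to all these figures.

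**The case against.** The strongest reply is that the rule does not bind. The DSMB may recommend a stop, must weigh risks, benefits and external evidence, and is told not to act on a single value. This stands. The crossing rates above are therefore not false-stop rates; the false-stop rate is lower and cannot be computed from the documents. But discretion does not take secondary outcomes off the list of stated grounds.

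A reader might infer that the trial would end at half size with the primary question unanswerable. The documents do not support that. Half describes the data analysed at the planned look, not enrolment at that date. Extending follow-up, dropping one arm and modifying the study are all among the DSMB's options. Neither document says that infants in mid-follow-up would be abandoned, or that they would be followed. A crossing on LAZ would also bear closely on length velocity, since LAZ at 6 months reflects attained length.

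A reader might also infer that maternal weight or MUAC would respond before infant length. Nothing in the documents shows this, and the point does not need it.

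The simulated rates depend on the model. Stunting, wasting and underweight are cut-points of LAZ, WLZ and WAZ, so some correlations would be higher than assumed, which lowers the rates. With only the two comparisons against control named in the protocol's analysis approach, the five-outcome figure is about 1.7–2.2%. SAP section 12 names Tukey's test for multiple comparisons. If it also applied at the interim, which section 15 does not say, it would cover arm pairs but not the number of outcomes. Under the protocol's own rule the excess is modest; under the SAP's it is large.

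**Conclusion.** The point holds as a defect in the stopping guideline. Both documents make a benefit on any one unnamed secondary outcome a stated ground for termination, with no supporting primary result and no correction for outcomes or arm pairs, in a trial sized only for length velocity. It makes a stop possible, not automatic.

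The cost to the primary depends on what happens to infants already enrolled. Power is 51–57% on the data analysed at the look, and about 63–80% if they are followed and accrual takes 36 to 12 months. The inflation in nominal crossings rests on the assumed correlations, three pairs and a single look. The two thresholds conflict and need to be reconciled as a separate matter; the endpoint problem exists under either.

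**What to change.** In both documents, delete the part of the benefit criterion that extends it to secondary outcomes, so that only length velocity can trigger stopping for benefit. State that secondary outcomes go to the DSMB as supporting information. Leave the harm criterion unchanged.

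This is a one-phrase amendment to the protocol and the SAP, and to any DSMB charter that repeats the wording. The price is that the trial could not stop early for a benefit seen only on a secondary outcome. Serious adverse events and deaths stay under the separate harm rule. Requiring a supporting primary result, or naming the secondary outcomes that count, would also narrow the gap, but deletion is simpler and needs no further error control across outcomes.

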11. SAMPLE SIZE CALCULATIONS & POWER ANALYSIS

The sample size is calculated and powered to look at multiple comparisons, between arms A and B, A and C plus B and C with a hypothesized higher increase with addition of Azithromycin to infant with Afzaaish in LW. Also, adjustment for multiple comparison is needed. Thus, calculations for the sample size is estimated and are per arm sample size is provided below based on the primary outcome of length velocity in LW trial with 1-sided testing, alphas to account for multiple comparison (the lower alpha), and drop out of 14% is assumed in the trial.

Assumptions for Sample Size Calculations

Variable	Difference	Std Dev	Alpha	Drop out portion	n/arm	n/arm adj dropout	Actual Power
Length Velocity	0.12	0.5	0.025	0.14	274	319	0.801

Based on assumptions, a sample size of 319 children per arm is calculated, assuming 14% drop out rate (i.e. 10% margin for loss to follow up, and 4% infants deaths).

This is a community-based, open-label, multiarm randomized controlled trial that will include parallel group assignments with a 1:1:1 allocation ratio in low-income squatter settlements in urban Karachi, Pakistan. The women in the control group (control arm) will receive standard counseling only, whereas the lactating women in the first intervention group (intervention arm 1) will receive two sachets of balanced energy-protein (BEP) supplementation per day from enrollment until the infant reaches six months of age. The lactating women in the second intervention group (intervention arm 2) will receive the same BEP supplementation as those in intervention arm 1 while their babies will also receive a single stat dose (20 mg/kg orally) of Azithromycin at 42 days.

2. Objectives

The primary objective is to compare the efficacy of fortified, balanced energy-protein (BEP) supplements being consumed by lactating women for 6 months (intervention arm 1) with or without a single prophylactic dose of oral azithromycin to the infant at 42 days of age (intervention arm 2) with that of standard exclusive breastfeeding and nutritional counseling alone (control arm) in improving length velocity among infants at 6 months (outcome). The secondary outcome is to compare the impact of the interventions on weight (or growth) velocity, Z-scores, other anthropometry measures of infants, maternal weight changes, breast milk quality, gut microbiota, and key micronutrient levels in both the mother and infant.

3. Study setting and study population

The trial is being conducted in the peri-urban communities of Karachi, Pakistan. The study population includes only lactating women of reproductive ages who have recently delivered and their infants. Lactating women between 13 and 49 years of age and their newborns are the study population.

4. Primary hypothesis

Length velocity at 6 months of infant's age

H_a = Mean difference in length velocity of $>0.12\text{cm/month}$ to look at comparisons between multiple arms

H_o = Mean difference in length velocity of $\leq 0.12\text{cm/month}$ to look at comparisons between multiple arms

5. Secondary hypothesis

Growth velocity at 6 months of infant's age

H_a = Mean difference in growth velocity of $>0.4\text{ gram/kg/day}$ to look at comparisons between multiple arms

H_o = Mean difference in growth velocity of $\leq 0.4\text{ gram/kg/day}$ to look at comparisons between multiple arms

Length-for-Age Z-score (LAZ) at 6 months of infant's age

H_a = Mean difference in LAZ >0.5 to look at comparisons between multiple arms

H_o = Mean difference in LAZ ≤ 0.5 to look at comparisons between multiple arms

Weight-for-Length Z-score (WLZ) at 6 months of infant's age

H_a = Mean difference in WLZ >0.5 to look at comparisons between multiple arms

H_o = Mean difference in WAZ ≤ 0.5 to look at comparisons between multiple arms

Weight-for-Age Z-score of (WAZ) at 6 months of infant's age

H_a = Mean difference in WAZ >0.5 to look at comparisons between multiple arms

H_o = Mean difference in WAZ ≤ 0.5 to look at comparisons between multiple arms

6. Sample Size

There are limited data available on the impact of BEP on length velocity over the first 6 months of life in infants. However, in one of the studies, the mothers received only perinatal supplement, and the overall increase in length (cm/month) was $\beta = 3.289$ among the LNS group and $\beta = 3.346$ among the MMN group. (1) However, the women in this trial received supplements with smaller doses/energy than the women in our study will receive, and the intervention time was also different, i.e., the perinatal period rather than the infancy period. Another study showed that the difference in length velocity (cm/month) was 0.02 between the MMN and IFA groups over the period of 0-18 months. (2) Therefore, in the absence of clear evidence on the impact of these

interventions, we hypothesized the effect size to be 0.12 cm/month. This is also based on learning through field experience; when severely malnourished lactating women (MUAC < 19.0 cm) were provided with chickpea-based ready-to-eat supplements (100 gm/day for 3 months), the difference was 0.06 cm/month at 3 months of age between these women and women who did not receive any supplements (unpublished data that was used purely for implementation and was not included in a study).

The null hypothesis for this trial is that the mean difference in length velocity between an infant of a lactating woman receiving standard breastfeeding counseling with BEP alone (Intervention arm 1) for 6 months or in combination with a single prophylactic dose of azithromycin at 42 days of age (Intervention arm 2) and an infant of a lactating woman receiving standard breastfeeding counseling alone (control arm) is equal or less than 0.12 cm/month (primary outcome). Due to the absence of evidence of such interventions on length velocity, we based this hypothesis on our local experience and field data from our field sites. The alternate hypothesis for this trial is that an infant of a lactating woman receiving BEP alone for 6 months or in combination with a single prophylactic dose of azithromycin at 42 days of age has a mean length velocity is greater than 0.12 cm/month that of an infant of a lactating woman not receiving an intervention at 6 months. The sample size takes multiple comparisons into account and is based on the primary outcome of length velocity with an effect size of difference of 0.12 cm per month between the arms (i.e., 0.72 cm difference at 6 months), a 1-sided test, power of 80% and an alpha of 0.025 to account for multiple comparisons (the lower alpha – Bonferroni correction was used). A drop-out rate of 14% (i.e., 10% loss to follow up and infant mortality rate of 4%) is assumed in the study, so the minimum total sample size required is 957 (319 lactating women in each arm).

7. Eligibility criteria

Inclusion Criteria

- a) Lactating women with a mid-upper-arm-circumference (MUAC) of < 23.0 cm
- b) Infants with a live birth outcome, captured within 168 hours (0-6 days)
- c) Individuals with the intention to stay in the catchment area for entire duration of trial after enrollment
- d) Individuals with the intention to exclusively breastfeed child for at least 6 months of age
- e) Individuals who have provided voluntary written informed consent

Exclusion Criteria

- a) Newborns with a birth weight of less than 1500 grams
- b) Newborns with a known congenital anomaly or other severe illness based on the study physician's assessment before enrollment.
- c) Lactating women with known allergies to peanut, lentils, chickpea or dairy products
- d) Individuals who were previously enrolled in the trial

8. Blinding

The outcome assessors will be blinded, responsible only for the anthropometry measurements, and will be assigned a schedule that does not overlap with those of the follow-up teams. All investigators will also be blinded to group allocation throughout the period of the study. Furthermore, a statistician will independently perform the interim analysis for the Data Safety and monitoring board (DSMB) blinded by arm. Furthermore, the data analyst who will perform the final analysis will be blinded, and the code will eventually be revealed after the blinded results are shared with DSMB and investigators in a final review meeting. This is an unblinded study so SAEs may be related to use of BEP, unlikely to be blinded.

9. Treatment allocation

Stratified block randomization with blocks of sizes 3, 6, and 9 is used. Sequence generation will be performed by an independent statistician using a random selection method before the beginning of the trial. Self-adhesive, pre-coded sticky labels with unique identification numbers will be applied to sealed opaque envelopes containing the coded randomization identification number and intervention name to ensure that the

randomization process and allocation are blinded. Baseline information regarding nutrition and exclusive breastfeeding will be recorded. Anthropometry measurements of both the mother and newborn will be performed. The allocation ratio is 1:1:1.

10. Outcomes variables

